7.4.2.11. Change from Week 52/Baseline in the UFS-QoL Score

Change from Week 52/Baseline in the UFS-QoL Bleeding and Pelvic Discomfort (BPD) Scale score, UFS-QoL Symptom Severity Scale score, UFS-QoL Revised Activities Scale, UFS-QoL subscale scores, and total scores during the randomized treatment period will be summarized using descriptive statistics by treatment group and by visit. The scores after the time of retreatment initiation with open-label relugolix + E2/NETA will not be included in the analysis for randomized treatment period.

The change from Week 52/Baseline in UFS-QoL scores during the cumulative treatment period will be summarized by visit.

In addition, the proportion of responders as measured by the BPD Scale score and Revised Activities Scale will be summarized, as described below. This analysis will be performed for randomized treatment period and cumulative treatment period separately.

Calculation of UFS-QoL Symptom Severity Scale Score

To calculate the Symptom Severity Scale score, a summed score is created for the items listed below and then the formula below the table is used to transform raw scores to a normalized score with a range of possible values from 0 to 100. This provides Symptom Severity Scale scores, where higher scores are indicative of greater symptom severity and lower scores indicate lower symptom severity.

Scale	Sum Item Values	Lowest and Highest Possible Raw Scores	Possible Raw Score Range
Symptom Severity	Sum 1 – 8	8, 40	32

Formula for Transformation of Symptom Severity Raw Scores:

$$\text{Transformed Scale} = \left[\frac{(\text{Actual raw score} - \text{lowest possible raw score})}{\text{Possible raw score range}} \right] \times 100$$

Calculation of UFS-QoL Bleeding and Pelvic Discomfort Scale Score

The UFS-QoL BPD Scale has been derived from the UFS-QoL Symptoms Scale; the derivation and validation of this new scale can be found in the MVT-601-3001/3002 SAP. The new scale consists of the following three symptoms proximal to uterine fibroids:

- Heavy bleeding during your menstrual period (Q1)
- Passing blood clots during your menstrual period (Q2)
- Feeling tightness or pressure in your pelvic area (Q5)

To calculate the score for the BPD Scale, a summed score of the items listed below is created and then the formula below the table is used to transform the raw score to a normalized score. This provides BPD Scale scores, where higher score values are indicative of greater symptom severity and lower scores will indicate minimal symptom severity (high scores = bad).

Sub-Scale	Sum Item Values	Lowest and Highest Possible Raw Scores	Possible Raw Score Range
Q1, Q2 and Q5	Sum 1,2,5	3, 15	12

Formula for Transformation of BPD Raw Scores:

$$\text{Transformed Scale} = \left[\frac{(\text{Actual raw score} - \text{lowest possible raw score})}{\text{Possible raw score range}} \right] \times 100$$

On the basis of transformed score for BPD Scale, change from Week 52/Baseline in the transformed score for BPD Scale at Week 76 and Week 104 will be defined as a secondary endpoint. The proportion of patients who are responders (defined as meeting a meaningful change threshold from Week 52/Baseline in the BPD Scale) at Week 76 and Week 104 on the transformed score for the BPD Scale will be summarized for each treatment group. The proposed responder threshold is a 20-point change. Details in the determination of the meaningful change in the BPD Scale can be found in the MVT-601-3001/3002 SAP Appendix 4.

As a descriptive assessment on robustness of the responder analysis, a plot of the cumulative distribution function (CDF) will be provided for each treatment group to display the change from

Week 52/Baseline to Week 76 and Week 104 in the transformed score for BPD Scale on the x-axis and cumulative percentage of patients experiencing up to that change on the y-axis.

Calculation of Other UFS-QoL Scale Scores and UFS-QoL Total Score

For the other UFS-QoL scales (concern, activities, revised activities, energy/mood, control, self-conscious, and sexual function), a summed score of the items listed below is created for each individual scale. To calculate the UFS-QoL total score, the values for each individual scale are summed. See Table 14 for details. Using the formula below the table, all raw scores are transformed to normalized scores. Higher scores are indicative of better health-related quality of life (high = good).

For endpoints evaluating a single question, the raw score is used in the analysis. The activity and revised activity domain scores will be summarized by treatment group.

Table 14: Formulas for Scoring and Transforming UFS-QoL Scale Scores and UFS-QoL Total Score

Scale	Sum Item Values	Lowest and Highest Possible Raw Scores	Possible Raw Score Range
Concern	9+15+22+28+32	5, 25	20
Activities	10+11+13+19+20+27+29	7, 35	28
Revised activities	11+13+19+20+27	5, 25	20
Energy/mood	12+17+23+24+25+31+35	7, 35	28
Control	14+16+26+30+34	5, 25	20
Self-conscious	18+21+33	3, 15	12
Sexual function	36+37	2, 10	8
HRQL TOTAL	Sum of 6 Subscale Scores ^a	29, 145	116

Abbreviations: HRQL = health-related quality of life; UFS-QoL = Uterine Fibroid Symptom and Health-Related Quality of Life (Questionnaire).

^a HRQL Total includes following scales: concern, activities, energy/mood, control, self-conscious, and sexual function.

Formula for Transformation of Raw Scores of Other Scale Scores:

$$\text{Transformed Scale} = \left[\frac{(\text{Highest possible raw score} - \text{Actual raw score})}{\text{Possible raw score range}} \right] \times 100$$

For revised activities, the proportion of patients who are responders (defined as meeting a meaningful change from Week 52/Baseline in the revised activity score) at Week 76 and Week 104 will be analyzed similarly to that for the change in BPD Scale score for each treatment group. The proposed responder threshold is a 20-point increase. Details of the determination of the meaningful change in the Revised Activities Scale score can be found in the MVT-601-3001/3002 SAP Appendix 5.

Missing Item Handling in UFS-QoL Score Calculation

For any scale analyses, if $< 50\%$ of the scale items are missing, the scale should be retained using the mean scale score of the items present. If $\geq 50\%$ of the items are missing, no scale score should be calculated; the subscale score will be considered missing.

8. PHARMACODYNAMIC ANALYSES

Pharmacodynamic data for the randomized withdrawal study consists of pre-dose estradiol serum concentration at Week 52/Baseline and Week 56 only. Estradiol concentration data will be listed and summarized using descriptive statistics (including absolute and change from Week 52/Baseline) by randomized withdrawal study treatment group at baseline and Week 56. The number and percentage of patients with individual estradiol concentration values will be summarized by treatment group at baseline and Week 56 according to the following categories.

- < 10 pg/mL, 10 to < 20 pg/mL, 20 to < 30 pg/mL, 30 to < 40 pg/mL, 40 to < 50 pg/mL, 50 to < 60 pg/mL, 60 to < 70 pg/mL, and ≥ 70 pg/mL
- < 20 pg/mL, 20 to < 50 pg/mL, and ≥ 50 pg/mL
- < 20 pg/mL, 20 to < 60 pg/mL, and ≥ 60 pg/mL

Estradiol concentration values below the limit of quantification will be set to half of the lower limit of quantification.

Follicle-stimulating hormone concentrations were collected at Week 76 in patients who have been amenorrheic since randomization and the concentration data will be listed and summarized using descriptive statistics.

9. SAFETY ANALYSES

Unless otherwise specified, safety analyses will be conducted using the safety population according to the actual treatment received by the patients in this randomized withdrawal study.

9.1. Adverse Events

Adverse events will be collected from the time of the first dose of randomized withdrawal study drug through the safety follow up visit approximately 30 days after the last dose of randomized withdrawal study drug (if no retreatment was initiated) or approximately 30 days after the last dose of retreatment drug (if the retreatment was initiated), or the date of initiation of another investigational agent or hormonal therapy (eg, elagolix, acotol) or surgical intervention (eg, uterine artery embolization), whichever occurs first. Serious adverse events reported to the investigator after the safety reporting period should be reported to the sponsor if the investigator assesses the event as related to study drug.

The severity of all treatment-emergent adverse events will be evaluated by the investigator based on the National Cancer Institute's Common Terminology Criteria for Adverse Events (CTCAE), v.5.0 dated 27 Nov 2017, and will be coded to preferred term and system organ class using MedDRA 24.0 or higher.

A treatment-emergent adverse event for cumulative treatment period (including the randomized treatment and the retreatment periods) is defined as any adverse event that onsets or worsens after administration of the first dose of randomized withdrawal study drug.

For patients who stayed on the randomized treatment till end of the study, a treatment-emergent adverse event for the randomized treatment period is defined as any adverse event that onsets or worsens after administration of the first dose of randomized withdrawal study drug. For patients who had the retreatment drug initiated, any adverse event that onsets or worsens after administration of the first dose of randomized withdrawal study drug and prior to the initiation of the retreatment drug is defined as treatment-emergent adverse event for the randomized treatment period.

For patients who started the retreatment drug, a treatment-emergent adverse event for the retreatment period is defined as any adverse event that onsets after the initiation of retreatment drug.

Adverse event summaries will be based on treatment-emergent adverse events in the randomized withdrawal study, unless otherwise specified. The summaries will mainly be done for the cumulative treatment period. Some selected summaries may be provided for the randomized withdraw period and the retreatment period separately. All adverse events will be listed in by-patient listings.

The following tabular summaries that include the number and percentage of patients will be provided for the cumulative treatment period:

- Overview of adverse events;
- All adverse events;
 - By SOC and PT;

- By decreasing frequency of PT;
- By SOC, PT, and maximum severity;
- Drug-related per investigator by SOC and PT;
- By time to onset, SOC and PT;
- Grade 3 or higher adverse events;
 - By SOC and PT;
 - By decreasing frequency of PT;
 - Drug-related per investigator by SOC and PT;
- Adverse events leading to study drug withdrawal;
 - By SOC and PT;
 - By decreasing frequency of PT;
- Adverse events leading to dose interruption;
 - By SOC and PT;
 - By decreasing frequency of PT;
- Adverse events resulting in fatal outcome;
 - By decreasing frequency of PT;
- Serious adverse events;
 - By SOC and PT;
 - By decreasing frequency of PT;
 - By SOC, PT, and maximum severity;
 - By SOC, PT, and relationship to study drug;
- Adverse events of special interest or clinical interest (ALT or AST $\geq 3 \times$ ULN);
 - By SOC, PT, and maximum severity;
 - By decreasing frequency of PT.
- Adverse events with first onset during the randomized withdrawal study;
 - By SOC and PT;
 - By decreasing frequency of PT.

Additionally, adverse event categories defined in [Table 15](#) will be summarized by decreasing frequency of PT for the cumulative treatment period.

The following tabular summaries that include the number and percentage of patients will be provided for the retreatment period:

- Overview of adverse events;

- All adverse events;
 - By SOC and PT;
 - By decreasing frequency of PT;
 - By time to onset, SOC and PT;
- Grade 3 or higher adverse events;
 - By SOC and PT;
 - By decreasing frequency of PT;
- Adverse events leading to study drug withdrawal;
 - By SOC and PT;
 - By decreasing frequency of PT;
- Serious adverse events;
 - By SOC and PT;
 - By decreasing frequency of PT;
- Adverse events of special clinical interest (ALT or AST $\geq 3 \times$ ULN);
 - By decreasing frequency of PT.

The adverse events which were ongoing at the time of randomization of the randomized withdrawal study will be summarized as specified below. Such adverse events were collected during the pivotal study and LTE study and they are considered pre-existing conditions for the randomized withdrawal study.

- All adverse events;
 - By SOC and PT;
 - By decreasing frequency of PT;
- Grade 3 or higher adverse events;
 - By SOC and PT;
 - By decreasing frequency of PT;

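### The retreatment-period definition of a treatment-emergent adverse event leaves out worsening, so the retreatment safety tables can under-count events that worsen on open-label relugolix + E2/NETA

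*SAP*

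**What the plan says.** SAP 9.1 (Adverse Events) gives separate treatment-emergent definitions for three periods.

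- **Cumulative period** (randomized plus retreatment): a treatment-emergent event "is defined as any adverse event that onsets or worsens after administration of the first dose of randomized withdrawal study drug".
- **Randomized period:** the same rule for women who stay on randomized drug. For women who are later retreated, it is an event that "onsets or worsens after administration of the first dose of randomized withdrawal study drug and prior to the initiation of the retreatment drug".
- **Retreatment period:** "any adverse event that onsets after the initiation of retreatment drug".

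The section then says what the tables contain: "Adverse event summaries will be based on treatment-emergent adverse events in the randomized withdrawal study, unless otherwise specified". It also says which period carries most of the reporting: "The summaries will mainly be done for the cumulative treatment period". A separate set is nevertheless promised: "The following tabular summaries that include the number and percentage of patients will be provided for the retreatment period". That set comprises an overview, all events, Grade 3 or higher events, events leading to withdrawal of study drug, serious events, and ALT or AST elevations of at least 3 × ULN. All adverse events also go into by-patient listings.

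**The concern.** Worsening is in the cumulative definition and in both versions of the randomized-period definition, but not in the retreatment definition. Nothing elsewhere in the SAP or protocol puts it back for that period.

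The retreatment tables should show what happens when women who have been off drug, or who relapsed on it, start open-label active treatment. Protocol 4.2 names assessment of retreatment as a purpose of the design, and SAP 4.2.4 sets up a Retreatment population partly for selected safety data. A mild event that was already present and becomes severe on open-label drug is the kind of signal those tables should carry. As written, the rule can leave it out of the Grade 3 or higher, serious and withdrawal tables for the period in which it became severe, serious or treatment-limiting.

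**Working it through.** No sample size, power or event count is involved, and the plan states no figure to reproduce. The check compares the definitions and then classifies typical event histories under each.

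**Step 1. Can onset be read to include worsening?** No. The other definitions in SAP 9.1 name both. The same section also plans a cumulative-period table restricted to events with first onset during this study, separate from the all-event tables. The SAP therefore treats onset as narrower than treatment-emergent.

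**Step 2. Classify an event kept as a single record with its original start date.**

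| Event history | Cumulative | Randomized period | Retreatment period, as written | Retreatment period, with worsening added |
|---|---|---|---|---|
| (a) Ongoing from the pivotal or extension study; first worsens on retreatment | Yes | No | No | Yes |
| (b) Begins in the randomized period; worsens on retreatment | Yes | Yes | No | Yes |
| (c) Begins on retreatment | Yes | No | Yes | Yes |

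History (a) falls outside both period-specific definitions. The randomized definition closes at the start of retreatment (an event must occur "prior to the initiation of the retreatment drug is defined as treatment-emergent adverse event for the randomized treatment period"), and the retreatment definition needs a new onset. History (b) is in the randomized period by its onset, but its worsening on open-label drug is not in the retreatment period.

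**Step 3. Trace to the tables.** The summaries are built on treatment-emergent events, and nothing in the list of retreatment tables overrides this. Histories (a) and (b) therefore drop out of every table in that set, including Grade 3 or higher, serious and withdrawal.

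**Step 4. Do the cumulative tables do the same job?** They keep the events but do not isolate re-exposure. SAP 4.2.3 groups safety data by actual treatment and counts a woman as a relugolix patient if she took relugolix during the randomized treatment period. SAP 4.3.5 defines the retreatment period separately, as time on the open-label drug. On that reading, a woman randomized to placebo stays in the placebo column of the cumulative tables after she starts open-label drug. That holds whatever the retreatment definition says; it means only that the cumulative tables cannot stand in for the retreatment tables.

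**The case against.** The strongest reply has three parts.

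**The events are not lost to the study.** This stands. The cumulative tables are the main adverse event summaries and they count worsening. They also include breakdowns by maximum severity and by drug relationship that the retreatment set lacks. The listings show every event. A reader might infer that the retreatment tables are the only safety display covering re-exposure; the documents do not support that. They are the only tables that separate it out.

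**Some worsenings may be captured anyway.** This stands in part. Protocol 7.1.1 counts a worsening of a pre-existing condition, beyond minor fluctuation, as an adverse event. If a site enters it as a new event with a new start date, it satisfies the retreatment definition. Neither document states that recording rule, and if it applied throughout, the mention of worsening in the other definitions would be largely redundant. So the SAP cannot rely on it, but nor can one say that every such worsening is lost.

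**The events are not shown to move to placebo.** This stands. A reader might infer that a worsening on open-label drug is reported against the placebo period. That needs a single record held at maximum grade and assigned to the earlier period, and a randomized-period table to receive it. Protocol 9.5 counts a repeated event once at maximum severity but does not say to which period. SAP 9.1 lists no randomized-period tables and says only that selected ones may be provided.

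**Conclusion.** The inconsistency is real and confined to the retreatment-period adverse event tables. As written, they exclude an event that began before retreatment and worsened on open-label drug, unless the worsening was entered as a new event. No efficacy analysis and no cumulative safety table is affected.

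The size cannot be computed. Depending on how sites recorded worsening, the loss lies anywhere from none to all of this class of event, and the documents give no adverse event rates and no retreatment counts.

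A reader might take the planning rates as a measure: 360 / 2 = 180 placebo women, with a 40% responder rate leaving 0.60 × 180 = 108 relapses by Week 76. If the 20% dropout is removed first, 180 × 0.80 = 144 and 0.60 × 144 ≈ 86. Neither figure measures this problem. Both count expected relapses, not women whose event worsens on retreatment. Retreatment can be declined, and the Retreatment population also includes relapsing women from the relugolix arm.

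**What to change.** In SAP 9.1, extend the retreatment definition to events that begin or worsen after the first dose of retreatment drug, using the date and grade of the worsening where they are recorded. The documents do not say that the eCRF captures dated grade changes, so the SAP should also say how an event is handled when only one record at one grade exists. An alternative is to state that a worsening is recorded as a new adverse event with its own start date, if that was the practice at sites.

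The cost is small: one change of wording and one derivation flag. An event of history (b) can then count in both the randomized and retreatment periods, which a table footnote should say. The cumulative tables and the other treatment-emergent definitions do not change.

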4.2.3. Safety Population

The Safety population consists of all patients who were randomized and took at least one dose of study treatment. All safety analyses will be performed using the safety population, unless otherwise specified. Safety data will be analyzed by treatment group according to the actual treatment received (not the randomized treatment). Any patient who received at least one dose of relugolix during the randomized treatment period will be considered as a relugolix patient.

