4.3. Definitions, Computation, and Convention

4.3.1. Definition of Date of First Dose and Date of Last Dose of Study Drug During the Randomized Treatment Period

The randomized treatment period is the period when a patient was on one of the randomized study drugs (relugolix + E2/NETA or placebo). The date of first dose of study drug is defined as the date when a patient receives the first dose of study drug for the randomized withdrawal study following randomization. The first dose of study drug for the randomized withdrawal study was to be self-administered the next morning following the Week 52/Baseline visit.

The date of the last dose of randomized study drug is defined as the date a patient receives the last dose of randomized study drug in this randomized withdrawal study, prior to re-treatment or on the Week 104 visit date. If the complete date of last dose of study drug is unknown, the last date the study drug was known to have been taken will be used.

4.3.2. Definition of Date of First Dose and Date of Last Dose of Retreatment Drug

The date of first dose of retreatment drug is defined as the date when a patient receives the first dose of retreatment drug (open-label relugolix + E2/NETA). When the return of heavy menstrual bleeding (defined as menstrual blood loss of ≥ 80 mL) was confirmed for a patient during the randomized treatment period, the patient was to be offered retreatment with open-label relugolix + E2/NETA with the onset of the next menses.

The date of the last dose of retreatment drug is defined as the date a patient receives the last dose of retreatment drug in this randomized withdrawal study, prior to or on the Week 104 visit date. If the complete date of last dose of retreatment drug is unknown, the last date the retreatment drug was known to have been taken will be used.

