4.3.5. Definition of Treatment Duration During the Retreatment Period

The retreatment period is the period when a patient was on the open-label retreatment drug. Treatment duration of retreatment drug is defined as the duration of time from the date of the first dose of retreatment drug to the date of the last dose of retreatment drug as follows:

$$(\text{Date of last dose of retreatment drug} - \text{Date of first dose of retreatment drug}) + 1$$

For patients without complete date of last dose of retreatment drug, the last date retreatment drug was known to have been taken will be used to calculate treatment duration. For patients who did not return for the Early Termination visits during the retreatment period, the time after their last visit will not be included in calculations of treatment duration.

The cumulative treatment period includes both the randomized treatment period and the retreatment period.

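### SAP 9.1 leaves randomized-period adverse event tables optional, so the committed relugolix-versus-placebo AE comparison mixes in open-label retreatment

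*SAP*

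**What the plan says.** SAP 9.1 defines treatment-emergent AEs separately for the cumulative, randomized and retreatment periods. For a retreated patient, an event after the first randomized dose and "prior to the initiation of the retreatment drug is defined as treatment-emergent adverse event for the randomized treatment period". On reporting it says: "The summaries will mainly be done for the cumulative treatment period. Some selected summaries may be provided for the randomized withdraw period", with the retreatment period under the same *may*.

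The lists that follow are firmer, but not for every period. One opens "The following tabular summaries that include the number and percentage of patients will be provided for the cumulative treatment period", another "The following tabular summaries that include the number and percentage of patients will be provided for the retreatment period", and a third covers AEs ongoing at randomization. The Table 15 categories (bone, hepatic, metabolic, vasomotor, mood) are committed for the cumulative period. No list is given for the randomized period.

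On periods and columns:

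- SAP 4.3.5: "The cumulative treatment period includes both the randomized treatment period and the retreatment period".
- SAP 4.2.3: "Any patient who received at least one dose of relugolix during the randomized treatment period will be considered as a relugolix patient".
- SAP 4.3.1: "The randomized treatment period is the period when a patient was on one of the randomized study drugs".
- SAP 9, more loosely, analyses safety "according to the actual treatment received by the patients in this randomized withdrawal study".

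**The concern.** Patients still on their randomized drug provide the only part of this study in which relugolix + E2/NETA is compared with placebo without crossover. Safety over up to a further 52 weeks is a stated objective. Yet the AE comparison for that part is optional, while the two-arm tables that are committed run on through open-label retreatment. A placebo patient who relapses and restarts relugolix seems to remain in the placebo column, with her on-drug events counted there.

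At stake is how the placebo column reads. For an AE whose excess persists while dosing continues, on-drug time counted as placebo narrows the difference between arms. A reader of the report could take a diluted contrast for reassurance.

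**Working it through.** **1. What is committed**

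| Period | Treatment-emergent AE defined | Tables | Relugolix-versus-placebo comparison |
|---|---|---|---|
| Cumulative | yes | committed | yes, but mixed with retreatment |
| Randomized | yes | optional | yes, unmixed |
| Retreatment | yes | committed | no, everyone is on open-label relugolix |
| Ongoing at randomization | treated as pre-existing | committed | no |

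The table of AEs with first onset during the study sits in the cumulative list and covers the whole study, so it does not fill the gap.

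**2. Which column.** Under SAP 4.2.3, relugolix makes a patient a relugolix patient if taken in the randomized period. Under 4.3.1 that period is time on randomized drug. A correctly dosed placebo patient who later takes open-label drug is therefore not moved. If the wording in SAP 9 were read as moving her, events from her placebo time would move with her.

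**3. Inputs.** SAP 2.2 plans 360 patients randomized 1:1, responder rates of 40% and 60%, 20% dropout and at least 90% power. With 180 × 0.8 = 144 per arm, power is 92.8%, so that figure reproduces and is not in dispute. I read the 40% as the placebo proportion relapse-free at 24 weeks. Relapse is dated to the earliest bleeding day of the heavy collection window (SAP 7.3.1.2), and retreatment waits for the next menses after the analysis (SAP 2.1). Zero delay is therefore excluded, and I assume d = 4 to 8 weeks. Relapse shape, uptake, AE risks and constant AE hazards are also assumptions.

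**4. Placebo-arm time on relugolix** (full uptake, no dropout): weeks on drug = max(0, 52 − relapse time − d), averaged over patients.

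- Constant hazard: λ = −ln(0.4)/24 = 0.0382 per week; mean weeks = (52 − d) − [1 − exp(−λ(52 − d))]/λ. For d = 4 this is 48 − 22.0 = 26.0 (50%); for d = 8 it is 44 − 21.3 = 22.7 (44%).
- Relapses uniform over weeks 4 to 24, none later: mean weeks = 0.6 × (52 − 14 − d). For d = 4 this is 20.4 (39%); for d = 8 it is 18.0 (35%).

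If only 80% accept and decliners leave at that point, the range is 0.8 × 18.0/(52 − 0.2 × 18.0) = 30% to 0.8 × 26.0/(52 − 0.2 × 26.0) = 44% of follow-up.

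**5. Effect on an AE.** Take 52-week risks of 20% on relugolix and 10% on placebo. Weekly hazards are −ln(0.8)/52 = 0.00429 and −ln(0.9)/52 = 0.00203. A placebo patient with r weeks on drug has risk 1 − exp[−0.00203(52 − r) − 0.00429r]. Averaging over r, and varying the 40%:

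| Placebo relapse-free at 24 weeks | Placebo-arm time on relugolix | Cumulative placebo column | Apparent risk ratio (true 2.0) |
|---|---|---|---|
| 20% | 46-65% | 14.7-16.6% | 1.2-1.4 |
| 40% | 35-50% | 13.5-15.1% | 1.3-1.5 |
| 60% | 23-34% | 12.4-13.5% | 1.5-1.6 |

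At 40% the difference is 4.9-6.5 points instead of 10.

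**6. The randomized-period table.** Follow-up is min(52, relapse time + d). With 40% and 60% relapse-free at 24 weeks, mean follow-up is 26.0 weeks on placebo and 34.1 on relugolix (constant hazard, d = 4), up to 34.0 and 40.0 (uniform, d = 8). Crude risks are 5.1-6.6% against 13.4-15.6%, a gap of 8.3-9.0 points. The rates are 10.6 and 22.4 first events per 100 patient-years. Crude percentages on unequal follow-up are not enough.

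**7. Bone mineral density (BMD).** Protocol 9.5 tabulates declines of at least 3, 4, 5, 6 or 7% by study treatment group. SAP 9.3.3.1 tabulates Week 52-to-104 categories by the arm of the pivotal study, with boundaries at 2, 3, 5 and 8%. Those bins cannot yield 4, 6 or 7%, and at 3% and 5% they use greater than, not at least.

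**The case against.** The column rule is inferred, and SAP 9 is loose enough to be read the other way. That stands as a caution about direction. It does not rescue the tables, since either reading mixes the columns.

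SAP 1.1 says the Table 1 endpoints, AE incidence included, will also be analysed over the combined period, which suggests the randomized period is the starting point. But that sentence defers to Section 9, and 9.1 makes randomized-period AE summaries optional.

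A reader might infer that no placebo-controlled AE comparison is committed at all. The documents do not support that. The cumulative tables, grouped as SAP 4.2.3 implies, are close to an as-randomized comparison with follow-up not cut at relapse: diluted, not absent. The committed time-to-onset table, if shown by arm, also helps in its early bins. Under the constant hazard above with a 4 to 8 week delay, nobody has restarted by week 4 and at most 1 − exp(−0.0382 × 4) = 14% by week 8. Bin widths are unspecified and later bins are mixed, so the relief is partial.

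A reader might also infer that the distortion always runs toward no difference. That needs an AE hazard that persists with dosing. These women have already had 28 or 52 weeks of relugolix; if events cluster at restart, retreated placebo patients could match or exceed continuing ones.

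Finally, the randomized-period table has its own flaw: follow-up ends after relapse. That is true, and it is why the cumulative tables should stay.

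**Conclusion.** The point holds as a gap in what is committed. Followed as written, every committed two-arm AE table mixes open-label relugolix time into a column, and the unmixed comparison is left to discretion although its treatment-emergent definition already exists. On the assumptions above, about a third to a half of placebo-arm time would be on relugolix at the planned 40%, and a true risk ratio of 2.0 would read as 1.3-1.5. Over 20-60% the ranges are 23-65% and about 1.2-1.6. These are illustrations: the documents give no AE rates, retreatment uptake or relapse timing.

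A breach of the protocol might be inferred, but is not shown. Protocol 9.5 runs the treatment-emergent period to about 30 days after the last dose and does not cut it at retreatment.

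The BMD items are separate and minor. The pivotal-arm grouping in SAP 9.3.3.1 is wrong as written and probably a drafting slip. One might extend the protocol's decline cuts to SAP 9.3.3.2, but the protocol sentence follows directly on change from Week 52/Baseline and does not clearly require them from the pivotal baseline.

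**What to change.** (a) In SAP 9.1, change *may* to *will* for a short list of randomized-period AE tables by randomized withdrawal group: overview, system organ class and preferred term, grade 3 or higher, serious, leading to withdrawal, ALT/AST ≥ 3 × ULN, and the Table 15 categories. Use the treatment-emergent definition already in 9.1 and add exposure-adjusted incidence. Keep the cumulative tables and state which column holds retreated placebo patients. A further split before and after retreatment is unnecessary once the randomized-period and retreatment tables both exist.

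(b) In SAP 9.3.3.1, tabulate the Week 52-to-104 BMD categories by randomized withdrawal treatment group.

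(c) In SAP 9.3.3.1 only, add the protocol's declines of at least 3, 4, 5, 6 and 7%.

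The cost is SAP wording and a few more tables. No new data are needed, because SAP 6 already summarizes treatment duration by period. Randomized-period follow-up remains linked to relapse, and exposure adjustment does not fully remove that link.
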